13.3.4 Collection of Ablation Procedure Data for Post-Analysis (non-SOC)

At the completion of the study ablation procedure, two back-up copies of the CARTO™ and generator system log files will be made. One copy should be kept at the site within the investigator site or patient binders, and one fully anonymized copy will be provided to/collected by the Sponsor.

13.3.5 Data Collection during Study Ablation Procedure

The following information will be collected during the procedure, including but not limited to:

Technical parameters are collected via CARTO™ datafiles and generator files, including but not limited to:

- Number of PF/RF applications
- Energy delivered
- PF/RF application time
- Ablation settings used
- Ablation information will be collected in the CARTO™ 3 system and investigational Generator
- Contact force values

Other procedural parameters are collected via Electronic Data Capture (EDC), including but not limited to:

- Use of a non-study catheter for PVI
- Number of PF/RF applications per left and right PV per left and right PV
- Number of PF/RF applications per target PV and by subject
- Number of PF/RF applications required with a non-study catheter
- PVI confirmed with BWI multi-electrode mapping catheter
- PV acute reconnection (early or dormant)
- Procedure time (from first femoral puncture to last catheter out)
- Mapping time (start mapping - end mapping)
- Total fluoroscopy time
- Total study catheter LA dwell time (from first study catheter insertion in LA until study catheter removal from LA)
- ECG data
- Total fluid delivered via study catheter
- Total fluid delivered via intravenous line (if captured)
- Fluid output (if captured)
- Device deficiency information (if applicable)
- Procedural medication (paralytics)
- Use of paralytics and type of anesthesia

13.3.6 Pre-Discharge Assessments

Prior to hospital discharge, the following assessments should be performed:

- **Medication regimen** (Cardiac, anti-coagulation, PPIs)
- Imaging assessment of **pericardial fluid** presence
- **AEs**
- **12- Lead -ECG**
- Additional Assessments for **NA subset** subjects (non-SOC): **Cerebral MRI, neurological exam and neurological evaluation using the NIH stroke scale** within 72-hours post procedure, preferable prior to discharge. A certified/qualified physician expert must perform neurologic exams at pre-and post-ablation and possibly at other follow-up visits, pending previous findings of micro-emboli/neurologic deficits. For procedures on Friday a window of a maximum of 96 hours is justified. Cerebral MRI images will be transmitted to an independent

core laboratory. NOTE: Patient questionnaires will only be used in countries with validated languages.

- Additional Assessments for **EE subset** subjects (non-SOC): **Endoscopy** to check for any esophageal lesions and/or damage will be performed preferable prior to discharge and no later than 72- hours after procedure (for procedures on Friday a window of a maximum of 96 hours is justified). Endoscopy images will be transmitted to an independent core laboratory.

13.4 Repeat Ablation Procedures

Repeat procedures may be performed at the discretion of the investigator. It is highly recommended to collect arrhythmia documentation (in example documented recurrences) before performing a repeat procedure.

Repeat procedures **during the blanking period** (\leq 90 days post index ablation procedure) must be conducted with the investigational device, with or without focal touch-up, if the arrhythmia is due to PV triggers. If the arrhythmia is due to non-PV triggers and the subject is treated with a commercially available ablation catheter and generator, the subject will be excluded from the long- term effectiveness cohort. Procedures for CTI dependent flutter in the follow up period are not considered repeat procedures per CIP.

Repeat procedures performed **after the blanking period** (\geq 90- 365days post index ablation procedure) may be managed per investigator discretion using a commercially available ablation catheter and generator.

For the repeat procedures, the investigator must collect and provide information on location of reconnections of PVs and in case of atrial flutter recurrence, confirm if CTI dependent flutter or not. The follow-up schedule will remain based on the index ablation procedure.

13.5 Post-Ablation Follow-up Schedule

The subjects will be required to complete follow-up visits through 12 months post index ablation procedure. Follow-up will be done at 7 days (phone call or clinic visit), 1, 3, 6 and 12 months (clinic visit). Follow-up visits should be scheduled according to the following timeframes: 1 month (1M 23-37), 3 months (3M, day 76-104), 6 months (6M, day 166-194) and 12 months (12M, day 335-379). Follow-up visit schedule should be based on the date of the index ablation procedure and will not reset if subject undergoes a repeat AF ablation procedure.

13.5.1 Seven (7) day follow-up visit

Discharged subjects will receive a **telephone call or** have a clinic **visit** at 7 days (7D, day 7-9) post ablation procedure to assess any occurrence of **Adverse Events** and any change in **medication regimen**. If subject is coming for a clinic visit at day 7, data from 12 lead ECG will be collected.

13.5.2 Monthly follow-up visit

At 1, 3, 6 and, 12-month follow-up visits, the following assessments will be performed:

- **Medical evaluation:**
 - AEs
 - Cardiac and anti-coagulation medication regimen
 - Cardiac related hospitalization and cardioversions
 - 12 Lead-ECG
- **As from 1-month: Atrial arrhythmia monitoring (non-SOC)**
 - **Remote Monitoring:** subjects will be provided with a remote monitoring device at the 1M FU visit and asked to record and transmit a minimum of 1 transmission (≥ 30 seconds) every week through the end of the month 5 of FU. Starting at month 6 of FU, subjects will be asked to record and transmit a minimum of 1 transmission (≥ 30 seconds) every month until the effectiveness evaluation period is completed (12 months post index ablation procedure). Subjects will also be asked to transmit any symptom-triggered episode that occurs from the time they receive the remote monitoring device through the 12M FU visit. Remote monitoring will be **conducted as follows:**
 - Distribution and start by month 1
 - <6 M: Weekly transmission of at least 1 scheduled recording
 - ≥ 6 M: Monthly transmission of at least 1 scheduled recording
 - Conduct and transmit recording whenever symptoms are present
 - **24 Hour Holter Monitoring:** per CIP a Holter monitor will be used at the 3-, 6- and 12-months follow-up visit to monitor the subjects' heart rhythm for 24 hours continuously. Following the 24h Holter, subjects will be contacted by the site to verify if symptoms are experienced during 24h Holter. An independent core laboratory will be used to evaluate and assess the remote and 24h Holter monitoring tracings.
- Additional Assessments for Cardiac **CT/MRA** subset subjects: A **cardiac CT/MRA** is required to be performed at the 3M FU (non-SOC) visit or any other point in time when the subject presents with symptoms of PV stenosis. For other subjects, a cardiac CT/MRA is only required to be performed if the subject presents with symptoms of PV stenosis.
- Additional Assessments for **NA** subset subjects (non-SOC): A **Cerebral MRI, Neurological Exam and Neurological Evaluation using the MMSE, NIHSS and mRS** are required to be performed if any neurological symptoms and/or cerebral ischemic lesions were identified at a prior evaluation.
NOTE: Patient questionnaires will only be used in countries with validated languages.

- Additional Assessments for **PVI Durability subset** subjects (non-SOC):
- A repeat electro anatomical creation of a paced activation map and bipolar voltage map will be performed by the ablating physician* in the enrolling hospital at 75 days (+/-15days) post index ablation procedure to verify isolation durability of the treated pulmonary vein during the index ablation procedure.
- A BWI multi-electrode mapping catheter should be used for the remap procedure. It is **REQUIRED** to use the same mapping catheter that was used during the index ablation procedure.
- Additional ablations may be performed at the discretion of the investigator.
- **NOTE***: preference to have the PVI durability assessment performed by the same ablation physician that treated the subject during index ablation procedure.

- **Quality of life** via the Atrial Fibrillation Effect on Quality-of-Life (AFEQT™) questionnaire (non-SOC), at Month 3, 6 and 12. **NOTE:** Patient questionnaires will only be used in countries with validated languages.

13.6 Early Termination Visit

If early termination of the study is required due to safety concerns, each site will undergo a monitoring visit to conclude any outstanding issues, collect all outstanding CRF information, verify device accountability, and discuss any other items relevant to the conclusion of the study. Any enrolled subjects will continue to be followed per the CIP requirements. In case of early termination due to safety concerns, reporting to EC and CA may be required per local regulations.

13.7 Unscheduled Visit

If a subject returns for a potential study related cardiovascular or neurological visit outside of the CIP -defined visit schedule provided in Table 3, the visit will be considered “unscheduled” (UNS). An investigator may request an unscheduled visit in the presence of a new or worsened cardiovascular condition or neurological deficit. If the unscheduled visit is for a repeat ablation procedure, the CIP follow-up schedule is based on the index ablation procedure. For all unscheduled visits, an unscheduled visit eCRF must be completed and the subject must also return for their next scheduled study visit per clinical investigational plan.

13.8 Core Laboratory for Evaluation

Independent central core laboratories and/or expert physician(s) will conduct objective evaluations of remote arrhythmia monitoring tracings, ECGs, Holter, Cerebral MRI, endoscopy and will evaluate PV stenosis of all subjects requiring the applicable assessments per CIP.

13.9 Schedule of Events Table

Table 3 displays the required schedule for subject treatments and evaluations.

Table 3: Summary of Subject Visits and Assessments

Assessments ²²	Pre-Procedure	Pre-Discharge	Follow-up					
			7 Day	1 Month	3 Month	6 Month	12 Month	UNS
Study Day			D7	D30	D90	D180	D365	
Visit window			D7-D9	D23-D37	D76-D104	D166-D194	D335-D379	
Clinic visit	●	●	● ⁶	●	●	●	●	● ²¹
Phone call			●					
Patient Informed Consent ¹	●							
Demographics	●							
Medical History ²	●							
Pregnancy test ³	●							
LA and LVEF assessment ⁴	●							
Left atrial thrombus detection ⁵	●							
Pericardial fluid assessment		●						
12 Lead ECG ⁶	●	●		●	●	●	●	● ²¹
Atrial Arrhythmia monitoring (Remote) ⁷				●	●	●	●	● ²¹
Atrial Arrhythmia monitoring (24-hour Holter) ⁸					●	●	●	● ²¹
Repeat ablations ⁹			●	●	●	●	●	● ²¹
Concomitant Medication ¹⁰	●	●	●	●	●	●	●	● ²¹
Device Deficiencies		●						
Adverse Events ¹¹	●	●	●	●	●	●	●	● ²¹
AFEQT ¹²	●				●	●	●	
Cardiac CT/MRA ¹³	●				● ¹³			
PV Durability Subset								
3D Electro anatomical mapping ¹⁴	●				● ¹⁴			
Endoscopy Subset								
Endoscopy		● ¹⁵						
Neurological Subset								
Cerebral MRI ¹⁶	● ¹⁸	● ¹⁹		● ²⁰	● ²⁰	● ²⁰	● ²⁰	● ²¹
Neurological Exam ¹⁷	● ¹⁸	● ¹⁹		● ²⁰	● ²⁰	● ²⁰	● ²⁰	● ²¹
NIH Stroke Scale ¹²	● ¹⁸	● ¹⁹		● ²⁰	● ²⁰	● ²⁰	● ²⁰	● ²¹
mRS	● ¹⁸			●	● ²⁰	● ²⁰	● ²⁰	● ²¹
MMSE ¹²	● ¹⁸			●	● ²⁰	● ²⁰	● ²⁰	● ²¹

1. Procedure must be done within 60 days of consent.
2. Medical history-including but not limited to arrhythmia, AAD therapy failure, heart disease (NYHA), vital signs, CHA2DS2 VASc Score and thromboembolic events.
3. In all women of childbearing age and potential. To be completed within 72-hours prior to ablation procedure.
4. Imaging within 6 months prior to procedure to assess the LA and LVEF, in case the imaging assessment is older than 6 months, LA/LVEF dimensions shall be re-measured during the index ablation procedure prior to insertion of the study catheter.
5. Performed the day before procedure or day of ablation procedure to rule out the presence of atrial thrombus using one of the following modalities TEE, ICE, CT, MRI.
6. Data from 12-lead ECG recordings will be collected (For pre-procedure, can be performed before ICF signature)
7. Arrhythmia monitoring via remote monitoring once per week as from 1-month follow-up visit to the end of 5-month follow-up and monthly as of 6-month follow-up visit and whenever subject feels symptoms.
8. Arrhythmia monitoring via 24H Holter, site to contact subject and verify if any symptoms experienced during the Holter monitoring.
9. Information on any repeat ablation after the index ablation procedure will be collected
10. Concomitant medication: only cardiac (i.e., anti-arrhythmia drugs, anticoagulation regimen) & index ablation procedure related (i.e., adenosine, anticoagulation (e.g., heparin, pain medication)

11. AEs must be collected from the time the subject signs the informed consent onward.
12. Patient questionnaires will only be used in countries with validated languages.
13. For all subjects: CT/MRA to be completed within 6 months prior to the index ablation procedure. Post procedure: for CT/MRA subset to be repeated at 3M FU, for all subjects CT/MRA to be repeated post procedure in case subject presents with PV stenosis symptoms.
14. For PV Durability subset: an electro anatomical map, activation and voltage re-map is to be performed pre and post procedure and to be repeated at 75 days post procedure (+/- 15 days).
15. For Endoscopy subset: Endoscopy preferable between 1 day to 3 days (72hours) post procedure. For procedures on Friday a window of a maximum of 96 hours is justified.
16. If observations are noted on the post-procedure MRI, the subject must have follow-up MRI at the next follow-up visit(s) until observations are resolved.
17. A certified/qualified physician expert must perform neurologic exams at pre-and post-ablation and possibly at other follow-up visits, pending previous findings of micro-emboli/neurologic deficits.
18. To be completed within 72-hours pre-procedure. For procedures on Monday a window of a maximum of 96 hours is justified.
19. To be completed within 72-hours post-procedure. For procedures on Friday a window of a maximum of 96 hours is justified.
20. Full neurological follow-up to be undertaken if neurologic symptoms and/or cerebral ischemic lesions identified in a prior evaluation.
21. If subject returns for a potential study related cardiovascular or neurological visit outside of the CIP defined visit schedule as deemed required per investigators discretion.
22. Assessments should not be repeated for the study if already done per standard of care within CIP defined time limits.

14 Assessment of Safety

14.1 Specific Safety Parameters

14.1.1 Definition of Adverse Events (AE)

An Adverse Event (AE) means any untoward medical occurrence, unintended disease or injury or any untoward clinical signs, including an abnormal laboratory finding, in subjects, users or other persons, in the context of a clinical investigation, whether or not related to the investigational device (MDR Article 2(57))

NOTE:

- a. *This definition includes events that are anticipated as well as unanticipated events*
- b. *This definition includes events occurring in the context of a clinical investigation related to the investigational device, the comparator or the procedures involved.*

Specifically, an AE is **any** undesirable experience (sign, symptom, illness, abnormal laboratory value, or other medical event) occurring to a subject during the course of the study, whether or not it is related to the investigational device or procedure. Physical findings (including vital signs) observed at follow-up, or pre-existing physical findings that worsen compared to baseline are considered AEs.

Any medical condition that is present at the time that the participant is screened will be considered as baseline and not reported as an AE. Such conditions should be added to background medical history, if not previously reported. However, if the study participant's condition deteriorates at any time during the study, it will be recorded as an AE.

[figure not shown]
Following arrhythmia's do not meet the definition of an AE:

- AF recurrence by itself is considered a recurrence of disease (pre-existing condition)
- Recurrence of pre-existing or underlying (treated during index ablation procedure) AFL/AT is considered as a recurrence of disease
- Onset of non-previously identified AFL/AT which was treated during the index ablation procedure as underlying arrhythmia (pre-existing condition)

- Re-ablation for AF or any pre-existing AFL/AT, however any procedural complication is considered an AE and shall be reported within the applicable timelines.
- Re-ablation for any non-pre-existing (underlying) AFL/AT, which was treated during the index ablation procedure, however any procedural complication is considered an AE and shall be reported within the applicable timelines.
- Cardioversion (pharmacological or synchronized electrical) for AF/AFL/AT recurrence during the hospitalization for the index ablation procedure, or throughout the duration of the study.

Following arrhythmia's meet the definition of an AE:

Onset of non-pre-existing AFL/AT which was not treated during the index ablation procedure.

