7.3.2 Secondary Hypothesized Endpoints

12-Month Effectiveness

Freedom from documented (symptomatic and asymptomatic) atrial arrhythmia (AF, AT or AFL of unknown origin*) episodes based on electrocardiographic data (≥ 30 seconds on arrhythmia monitoring device) during the effectiveness evaluation period (Day 91-Day 365) on or off antiarrhythmic therapy. Acute procedural failure (i.e., failure to achieve entrance block with the study device in any of the clinically relevant targeted PVs) will also be deemed a 12-month effectiveness failure.

**AFL of unknown origin is defined as all AFL except those CTI dependent AFL as confirmed by 12-lead electrocardiogram (ECG) or entrainment maneuvers in an EP study.*

Further refer to Appendix 2 for definitions on effectiveness terms.

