AdmIRE	NCT05293639	Biosense Webster, Inc.	TRUPULSE™ Generator VARIPULSE™ Bi-Directional Catheter	D-1417-01-I (TRUPULSE™ Generator) D-1412-01-SI (VARIPULSE™ Bi-Directional Catheter)	The VARIPULSE™ Catheter is indicated for use in catheter based cardiac electrophysiological mapping (stimulating and recording) and, when used with a TRUPULSE™ Generator, for cardiac ablation. The catheter provides location information when used with the CARTO™ 3 System. TRUPULSE™ Generator is indicated for use in conjunction with compatible cardiac ablation catheters to deliver pulsed field (PF) and radiofrequency (RF) energy during cardiac ablation procedures.	Adult patients with symptomatic paroxysmal atrial fibrillations	The VARIPULSE™ Catheter is non-implanted sterile catheter intended for single-patient, single-use only. There is no specific limitation in duration of use. The therapeutic device lifetime is the length of the procedure. Traditional point-by-point cardiac RF ablation typically last 2 to 4 hours. The TRUPULSE™ Generator is a reusable non-patient contacting device. There is no specific limitation in duration of use. The therapeutic device lifetime is the length of the procedure.	The study was conducted at 30 US sites with the total enrollment of 362 subjects.

30 Appendix 2

Definitions on effectiveness terms are mentioned below

Term	Definition
Recurrent AF/AT/AFL	Recurrent AF/AFL/AT is defined as AF/AFL/AT of at least 30 seconds' duration that is documented by an ECG or device recording system and occurs following catheter ablation. Recurrent AF/AFL/AT may occur within or following the post ablation blanking period. Recurrent AF/AFL/AT that occurs within the post-ablation blanking period is not considered a failure of AF ablation.
Early recurrence of AF/AFL/AT	Early recurrence of AF/AFL/AT is defined as a recurrence of atrial fibrillation within three months of ablation. Episodes of atrial tachycardia or atrial flutter should also be classified as a "recurrence." These are not counted toward the success rate if a blanking period is specified.

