#### 7.4.3 Secondary Effectiveness Endpoint

The secondary effectiveness endpoint is freedom from documented (symptomatic and asymptomatic) atrial arrhythmia episodes including atrial fibrillation (AF), atrial tachycardia (AT), or atrial flutter (AFL) of unknown origin\* during the effectiveness evaluation period (Day 91-365). The AF/AT/AFL episodes will be identified based on electrocardiographic data.

Subjects with an AF/AT/AFL episode that is  $\geq 30$  seconds on arrhythmia monitoring device during the evaluation period device are considered failures of this long-term effectiveness endpoint. Acute procedural failure (i.e., failure to achieve entrance block with the study device in any of the targeted PVs) will also be deemed a failure of this endpoint.

To evaluate the secondary objective of the study, the 12-month effectiveness success rate will be compared against a PG of 50%. The formal hypotheses to test the secondary effectiveness endpoint is given as follows:

$$H_0: P_1 \leq 0.50 \quad \text{vs} \quad H_A: P_1 > 0.50$$

where  $P_1$  denotes the the proportion of subjects who are failure-free at 12-month follow-up.

\*AFL of unknown origin is defined as all AFL except those CTI dependent AFL as confirmed by 12-lead electrocardiogram (ECG) or entrainment maneuvers in an EP study.

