##### 7.4.4.3 Additional Effectiveness Endpoints

- **Single Procedural Success:** defined as freedom from documented symptomatic atrial arrhythmia (AF, AT or AFL of unknown origin\*) episodes based on electrocardiographic data ( $\geq 30$  seconds on arrhythmia monitoring device) during the effectiveness evaluation period (Day 91-Day 365) following a single index ablation procedure. Subjects who had repeat procedure(s) for the study arrhythmia post the index procedure will be deemed failures of this endpoint.
- **Freedom from documented symptomatic atrial arrhythmia (AF, AT or AFL of unknown origin\*):** defined as freedom from the documented symptomatic atrial arrhythmia (AF, AT or AFL of unknown origin\*) recurrence

based on electrocardiographic data ( $\geq 30$  seconds on arrhythmia monitoring device) during the effectiveness evaluation period (Day 91-Day 365).

Acute procedural failure (i.e., failure to confirm entrance block in all PVs except those that are silent and/or cannot be cannulated post-procedure, use of non-study catheter for PV isolation, and failure to have energy delivery with the study device due to ablation system malfunctions) will also be considered a failure.

- **Freedom from documented (symptomatic and asymptomatic) atrial arrhythmia (AF, AT or AFL of unknown origin\*) with additional failure modes:** defined as freedom from documented (symptomatic and asymptomatic) atrial arrhythmia (AF, AT or AFL of unknown origin\*) based on electrocardiographic data ( $\geq 30$  seconds on arrhythmia monitoring device) during the effectiveness evaluation period (Day 91-Day 365). The following criteria will also be deemed failures:
  - Failure to achieve acute procedural success.
  - Taking a new Antiarrhythmic Drug (AAD) (Class I / Class III) for atrial tachyarrhythmia (AF, AT or AFL of unknown origin\*) or taking a previously failed Class I/III AAD at a greater than the highest ineffective historical dose for AF/AFL/AT during the effectiveness evaluation period (Day of 3-month visit\* – Day 365).
  - Greater than 1 repeat ablation for AF/AT or AFL of unknown origin\* in the blanking period or any repeat ablation for AF/AT or AFL of unknown origin\* during the effectiveness evaluation period.

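### Cardioversions are recorded at follow-up but count as a failure in no effectiveness endpoint and are not tabulated, so a subject cardioverted on Day 91-365 without a qualifying recording would count as a 12-month success

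*Protocol*

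**What the plan says.** - **Adverse events.** Protocol 14.1.1 lists as not being adverse events AF recurrence, re-ablation for AF or pre-existing AFL/AT, and "Cardioversion (pharmacological or synchronized electrical) for AF/AFL/AT recurrence during the hospitalization for the index ablation procedure, or throughout the duration of the study". One arrhythmia stays reportable: "Onset of non-pre-existing AFL/AT which was not treated during the index ablation procedure".
- **Data collection.** Protocol 13.5.2 includes "Cardiac related hospitalization and cardioversions" in the medical evaluation at the 1-, 3-, 6- and 12-month visits.
- **Gated 12-month endpoint.** Protocol 7.3.2 requires freedom from documented AF, AT or AFL of unknown origin of at least 30 "seconds on arrhythmia monitoring device) during the effectiveness evaluation period (Day 91-Day 365) on or off antiarrhythmic therapy". SAP 7.4.3 says that subjects with such an episode "are considered failures of this long-term effectiveness endpoint". The one other failure route is acute procedural failure, that is, "failure to achieve entrance block with the study device in any of the targeted PVs".
- **Extra-failure-modes endpoint.** In SAP 7.4.4.3, "The following criteria will also be deemed failures" introduces three items: no acute success, new or higher-dose Class I/III AAD, and repeat ablation (more than one in blanking, any afterwards). Protocol 7.3.3 has the same three. Cardioversion is not among them.
- **Definition of recurrence.** Protocol Appendix 2 accepts an episode of at least 30 seconds' "duration that is documented by an ECG or device recording system and occurs following catheter ablation".
- **Tabulation.** SAP 7.11.3 tabulates repeat ablation during and after blanking, with a Kaplan-Meier curve. The SAP does not mention cardioversion.

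**The concern.** Protocol 14.1.1 describes cardioversion as treatment of a recurrence and has it in the same list as re-ablation. The two then part. Re-ablation after blanking is a failure in the extra-failure-modes endpoint and is tabulated. It needs no tracing to count, since Protocol 13.4 only recommends collecting arrhythmia documentation beforehand. Cardioversion is recorded and then used nowhere, and no reason is given.

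At stake is the classification of a subject who was cardioverted for AF, AT or AFL of unknown origin on Day 91-365 and whose arrhythmia has no qualifying recording. Neither endpoint has a rule that fails this subject. In a single-arm comparison with a fixed goal, every such subject moves the success rate the same way, upwards.

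**Working it through.** **1. Which cardioverted subjects can be counted as successes?**

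| Subject cardioverted on Day 91-365 for AF, AT or AFL of unknown origin | Gated 12-month endpoint | Extra-failure-modes endpoint |
|---|---|---|
| Qualifying recording of at least 30 s | Failure | Failure |
| No qualifying recording; electrical | Not a failure | Not a failure |
| No qualifying recording; pharmacological, with a new or higher-dose Class I/III AAD | Not a failure (endpoint is on or off AAD) | Can be a failure, from Day 105 (note in SAP 7.4.4.3) |

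The gap is the second row, and the third row for the gated endpoint. It assumes no other failure and enough follow-up for a non-missing outcome (SAP 7.8.3).

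**2. The plan's own power figure.** The inputs are in Protocol 19.2: goal 50%, assumed rate 65%, 100 subjects less 10% = 90 analysed, one-sided exact binomial at 0.025. The critical value r is the smallest value with P(X ≥ r | n, 0.50) ≤ 0.025.

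- n = 90: r = 55, attained alpha 0.0223, power P(X ≥ 55 | 90, 0.65) = 0.812. The stated power of above 80% reproduces.
- n = 121 (135 × 0.90 = 121.5, rounded down): r = 72, attained alpha 0.0225, power 0.912. The exact lower 95% bound is 0.502 at 72 successes and 0.494 at 71.

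**3. Effect of the gap on the chance of passing.** Let d be the share of analysed subjects in the gap. The documents give no value, so d is an assumption, and 0% is possible. Suppose the success rate with these cardioversions counted as failures is exactly 50%. The plan then counts 50% + d, and the chance of passing is P(X ≥ r | n, 0.50 + d).

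| d (assumed) | n = 121, r = 72 | n = 90, r = 55 |
|---|---|---|
| 0% | 2.3% | 2.2% |
| 1% | 3.7% | 3.4% |
| 3% | 8.9% | 7.5% |
| 5% | 18.3% | 14.5% |

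At n = 121, d = 1% is about 1 subject (0.01 × 121 = 1.2) and d = 5% about 6 (0.05 × 121 = 6.05).

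**4. Effect of counting these subjects as failures.** If the rate under the present definition is the assumed 65%, the chance that an analysis counting the gap as failures still clears 50% is P(X ≥ r | n, 0.65 − d).

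| d (assumed) | n = 121 | n = 90 |
|---|---|---|
| 0% | 91.2% | 81.2% |
| 1% | 86.9% | 75.4% |
| 2% | 81.4% | 68.7% |
| 3% | 74.6% | 61.4% |
| 5% | 58.3% | 46.0% |

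**The case against.** The strongest reply is that the arrhythmia, not the cardioversion, is the endpoint event. Once AF, AT or AFL of unknown origin of at least 30 seconds is documented on Day 91-365, the subject fails. Documentation is not limited to scheduled recordings: subjects are asked to transmit symptomatic episodes (Protocol 13.5.2), the unscheduled-visit column of the schedule in 13.9 carries ECG, remote and Holter monitoring, and Appendix 2 accepts an ECG. An arrhythmia that leads to cardioversion is likely to leave a tracing. This stands, and it may make the gap small or empty. It does not close it. Symptom strips depend on the subject, unscheduled visits are at the investigator's discretion, and no passage makes a 30-second recording a condition for cardioversion or says how a case without one is classified.

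A reader might infer that the adverse-event exemption is what lets a cardioverted subject count as a success. The documents do not support that. The same list exempts AF recurrence, which is the core 12-month failure, and re-ablation, which is an extra failure mode. Adverse-event status does not decide effectiveness status.

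Cardioversion is also not wholly invisible. Some pharmacological cases can fail through the AAD item, and qualifying admissions enter the cardiovascular hospitalization summary. But the AAD item does not reach electrical cardioversion. The hospitalization endpoint needs an in-patient stay of more than one calendar day apart from the index admission (note in Protocol 7.3.3), so a same-day cardioversion is missed, and it is descriptive only.

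Finally, making an undocumented cardioversion a failure of the gated endpoint would change an endpoint built on electrocardiographic documentation. That is a debatable design choice, and the fix below does not ask for it.

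**Conclusion.** The point holds in a limited form. Cardioversion is recorded but is not a stand-alone failure criterion in any effectiveness endpoint and is not tabulated. A subject cardioverted on Day 91-365 without a qualifying recording, and without another failure, would be counted as a success in the 12-month endpoint and, unless the AAD item applies, in the extra-failure-modes endpoint.

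The direction is certain: misclassification can only raise the success rate. The size is not known. The rise from 2.3% to 18.3% in the chance of passing at n = 121 rests on assumed shares of 0% to 5% and on a true rate exactly at the goal. If every cardioverted episode has a qualifying recording, nothing changes. It would therefore go too far to say that the reported success rates are biased upward as a matter of fact, or that cardioverted subjects in general pass as successes.

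A second, smaller point also stands. The endpoint text speaks of an arrhythmia monitoring device, whereas Appendix 2 accepts an ECG or a device recording system. Whether a hospital ECG taken before cardioversion qualifies depends on which wording governs.

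**What to change.** 1. In Protocol 7.3.3 and SAP 7.4.4.3, add to the failure list of the extra-failure-modes endpoint: cardioversion (electrical or pharmacological) for AF, AT or AFL of unknown origin on Day 91-365.
2. Keep the gated 12-month endpoint as defined. In SAP 7.10, add a sensitivity analysis that counts such cardioversions as failures.
3. Reconcile the wording of a qualifying recording in Protocol 7.3.2 and SAP 7.4.3 with Protocol Appendix 2, and state whether a clinical ECG of at least 30 seconds counts.
4. In SAP 7.11.3, tabulate cardioversions in the blanking period and on Day 91-365, as is done for repeat ablation.

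**Cost.** The alpha and power of the gated test do not change. Success rates in the extra-failure-modes endpoint and the sensitivity analysis may be lower, and the sensitivity analysis may miss 50% when the gated test passes (step 4 of the working). The visit schedule already asks for cardioversions, but the documents do not show that the date and treated rhythm are captured. The eCRF must hold both, so that blanking-period procedures and CTI-dependent flutter can be separated out.
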